13.2 Urine Ethyl Glucuronide

Urine will be collected for ethyl glucuronide testing at screening, 1 week after induction (Safety Visit), and 4, 8, 12, and 16 weeks (or end-of-medication/end-of-treatment visit if medication or TAU intervention is stopped early) for assessment of secondary outcomes. Ethyl glucuronide is a biomarker of alcohol consumption in the previous 22 to 31 hours and will be used to confirm self-reported alcohol abstinence (Dahl, Stephanson et al. 2002; Wurst and Metzger 2002).

13.3 Addiction Severity Index-lite (ASI-Lite)

The ASI-Lite is derived from the Fifth Edition of the ASI (McLellan, Kushner et al. 1992), a structured clinical interview that yields scores for seven areas of functioning typically impacted by addiction, including medical status, employment status, drug use, alcohol use, family status, legal status, and psychiatric status. Only the drug use and alcohol use sections of the ASI-Lite will be used. Opioid and alcohol use questions, including the main type of opioid used by the participant, whether a prescription opioid or heroin, the onset of the use, the participant's perception of the substance that is most problematic, and their present treatment goal will also be assessed at baseline as part of the ASI-Lite assessment. The ASI-Lite drug and alcohol sections will be completed at baseline and 16 weeks (or end of medication/end-of-treatment visit if medication or TAU intervention is stopped early) for assessment of secondary outcomes.

13.4 Timeline Follow Back (TLFB)

Timeline Follow Back (TLFB) assesses self-reported drug and alcohol use over the past 30 days, with high test-retest reliability and validity (Sobell and Sobell 1992; Sobell and Sobell 2000). Participants will be asked to report daily drug and alcohol use since the last visit at baseline, induction onto study medication, 1 week after induction (Safety Visit), and at 4, 8, 12, and 16 weeks (or the end-of- medication/end-of-treatment visit if medication or TAU intervention is stopped early) for assessment of secondary outcomes.

13.5 Visual Analog Craving Scale (VAS)

Participants' craving for opioids, and alcohol will be documented on a visual analog scale (VAS) that ranges from 0 (no craving) to 100 (most intense craving possible). Participants will be instructed specifically to indicate the overall intensity of craving experienced This scale will be completed at baseline and at 4, 8, 12, and 16 weeks (or the end-of- medication/end-of-treatment visit if medication or TAU intervention is stopped early) for assessment of secondary outcomes.

13.6 Treatment Services Review (TSR), Version 6 (28 days)

Select items from the Treatment Services Review, Version 6 (TSR-6) addiction treatment modules will be used to collect data on the number of counseling sessions attended in the past

28 days, as well as detoxification, outpatient, inpatient, and medication-assisted addiction treatment services (Cacciola, Alterman et al. 2008). Participants will complete TSR-6 at baseline, treatment initiation, and 4, 8, 12, and 16 weeks (or end-of-medication/end-of-treatment if medication or TAU intervention stopped early) for assessment of TAU and counseling exposure in both TAU and XR-NTX arms.

13.7 Medication-Assisted Treatment

In order to assess study drug and other medication-assisted treatment exposure, TSR-6 responses will be augmented regarding use of medications for treatment of addiction with additional items asking specifically about use of XR-NTX, methadone, buprenorphine, disulfiram, and acamprosate during the past 28 days for participants randomized to both TAU and XR-NTX arms. Participants will be asked to report the number of days in the past 28 days that each medication was taken at least once per day. This information will be collected from participants at baseline, Week 0, 4, 8, 12, and 16 (or end-of-medication/end-of-treatment if medication or TAU intervention stopped early). Additional information gleaned from medical record review, to assess the dose and number of days of treatment prescribed for each medication will further augment this assessment.

13.8 Concise Health Risk Tracking - Self Report (CHRT-SR) Suicidal Behavior Evaluation

The CHRT-SR (Trivedi, Wisniewski et al. 2011) is a 16-item participant self-report assessment of suicidality and related thoughts and behaviors. The scale is designed to quickly and easily track suicidality in a manner consistent with the Columbia Classification Algorithm of Suicide Assessment (C-CASA) (Posner et al, 2007). The CHRT-SR will be assessed at baseline, Week 0, and 1, 4, 8, 12, and 16 week visits (or end-of-medication/end-of-treatment if medication or TAU intervention stopped early). The CHRT-SR will assess high risk suicide ideation by a positive response (Agree or Strongly Agree) on any of the last three questions (thoughts of, thoughts of how and/or a specific plan to commit suicide) and prompt a clinician assessment for suicide risk before leaving the clinic.

13.9 Concise Health Risk Tracking - Clinician Rated

Clinician Rated (CHRT-CR (Trivedi, Wisniewski et al. 2011). This assessment will be performed by the medical clinician only if a participant answers any of questions 14-16 on the CHRT-SR as agree or strongly agree as described above.

13.10 Readiness for Drug Treatment

Participants' attitudes toward and readiness for drug treatment will be measured by a 4 item readiness scale (Longshore and Teruya 2006) and a 4 item-negative attitudes scale (Conner, Longshore et al. 2009) both of which have good reliability in prior studies and relationships with treatment retention. Readiness for drug treatment is hypothesized to be a potential predictor of response to study drug treatment. It will be assessed at baseline and 16 week (or end-of- medication/end-of-treatment if medication or TAU intervention stopped early).

14.0 HIV RELATED MEASURES

14.1 Antiretroviral Medication Prescription and Adherence

Since HIV viral suppression is most strongly influenced by optimal use of ART, evaluation of adherence to one's ART regimen is essential. Self-reported antiretroviral use and adherence will be assessed with the AIDS Clinical Trials Group (ACTG) Adherence Questionnaire for measuring antiretroviral adherence (Reynolds, Sun et al. 2007) at baseline, Week 0, and 4, 8, 12, and 16 weeks or the end-of-medication visit (if medication is stopped early) for assessment of secondary outcome if participant is prescribed ART at the time of follow up visits. The ACTG questionnaire asks the participant to list each prescribed antiretroviral medication and then asks about adherence to each medication yesterday, 2, 3, and 4 days ago, adherence to schedule, instructions, during the last weekend and when any medication was last skipped. The questionnaire's responses are weighted to calculate an adherence level from 0 - 100 (Chesney, Ickovics et al. 2000; Reynolds, Sun et al. 2007). We will assess the proportion of participants taking 100% of prescribed ART doses in the past 3 days at 16 weeks for those prescribed ART at any point during the 16 week trial (proportion; self-reported ACTG adherence measure).

Because self-reported use of specific antiretrovirals has limited reliability when compared with medical record review (Korthuis, Asch et al. 2002; Brouwer, Napravnik et al. 2011), we will confirm ART use with medical record review at baseline and 16 weeks to assess the secondary outcome of ART prescription. Specifically, we will assess change in the proportion of participants prescribed ART within 16 weeks following randomization, compared to baseline (binary; medical record abstraction).

14.2 HIV Care Utilization

Will assess the number of HIV primary care visits at baseline and 16 weeks (count, chart abstraction).

14.3 HIV Risk Assessment Battery

The Risk Assessment Battery (RAB) (Navaline, Snider et al. 1994) is a self-administered assessment of engagement in activities that increase the likelihood of HIV transmission only sexual and drug-related HIV risk behavior items will be included, in an effort to limit instrument redundancy and participant response burden. Several scores that measure drug risk, sex risk, and total risk will be computed. It will be assessed at baseline, and 4, 8, 12, and 16 weeks (or the end-of-medication visit if medication is stopped early).

15.0 SAFETY ASSESSMENTS

15.1 Adverse Events, including Serious Adverse Events, and Protocol Deviations

Adverse Events, Serious Adverse Events, and Protocol Deviations will be assessed and documented.

Study staff members will assess for any medical or psychiatric side effects, by asking: “How have you been feeling since your last visit?” AEs will be solicited at each study visit, but will be recorded at any visit after consent when reported by the participant according to the adverse event reporting definitions and procedures outlined in the protocol.

If a reported AE suggests medical or psychological deterioration, it will be brought to the attention of the study medical clinician for further evaluation. SAEs will be medically managed, reported, and followed in accordance with applicable regulatory requirements. Safety assessments will be performed at all visits.

15.2 Non-Fatal Overdose

Non-fatal overdoses in the past 4 weeks will be assessed using a self-reported instrument used in previous studies at baseline and 16 weeks or the end-of-medication visit (if medication is stopped early) (Coffin, Tracy et al. 2007). Overdose events are sentinel events that are less likely to be prone to recall bias than other events. If non-fatal overdose resulted in adverse event, it should also be captured on the AE/SAE CRF.

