Aim 4: Assess the feasibility of integrating XR-NTX for opioid and alcohol use disorders into HIV clinics. Data collection during study start-up will inform selection of 2 HIV clinics to implement XR-NTX treatment. HIV providers and staff will be trained in detoxification and XR-NTX induction and management. HIV-infected subjects with untreated opioid and/or alcohol use disorders will be randomized to XR-NTX or TAU, followed by detoxification (if needed) and treatment induction. The primary outcomes are 1) treatment initiation (successful treatment initiation of XR-NTX or TAU within 4 weeks of randomization), and 2) retention on treatment condition at 16 weeks. Secondary outcomes include change in 1) HIV-1 RNA viral suppression, 2) Illicit drug and alcohol use, 3) HIV care engagement (receipt of ART, HIV visit adherence, ART adherence), and safety (percent with precipitated withdrawal, hepatotoxicity, or overdose).

Aim 4 Pilot Objective A: Estimate effect size point estimates for rate of treatment initiation and 16 week retention among HIV-infected patients with alcohol or opioid use disorders randomized to XR-NTX vs. TAU.

Aim 4 Pilot Objective B: Estimate effect size point estimates for secondary outcomes of HIV-1 RNA viral suppression, illicit drug and alcohol use, HIV care engagement, and safety among HIV-infected patients with alcohol or opioid use disorders randomized to XR-NTX vs. TAU.

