8.2 Secondary Outcome Measures

1) HIV outcomes:

- a) HIV-1 RNA viral suppression (plasma HIV-1 RNA pcr < 200 copies/mL) at 16 weeks compared with screening (binary, laboratory assay).
- b) Change in CD4 count at 16 weeks following treatment initiation compared with screening (count; laboratory measurement).

2) Substance Use:

- a) Change in 30 day opioid abstinence (by Addiction Severity Index (ASI)-lite self-report, Time-Line Follow-Back (TLFB) and urine drug screen (UDS) confirmation) in the final 30 days of the 16 week trial compared to screening (binary; laboratory data and self-report).
- b) Change in past 30-day alcohol and other drug use by ASI-lite, TLFB and UDS at week 16 visit, compared to screening (binary; laboratory data and self-report).

3) Engagement in HIV Care:

- a) Change in the proportion of participants prescribed ART within 16 weeks following randomization, compared to baseline (binary; medical record abstraction).
- b) Proportion of participants taking 100% of prescribed ART doses in the past 3 days at 16 weeks for those prescribed ART at any point during the 16 week trial (proportion; self-reported ACTG adherence measure).
- c) Number of HIV primary care visits at 16 weeks (count, chart abstraction).

4) Participant safety:

- a) Change in liver enzymes between screening and week 16 visit (laboratory assay).
- b) Any fatal and non-fatal opioid overdose between screening and week 16 (binary; medical record abstraction and self-report).
- c) Change in Concise Health Risk Tracking score between screening and week 16 visit (continuous; self-report).
- d) Proportion of participants assigned to XR-NTX who develop precipitated opioid withdrawal.

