10.1 List of all CRF's and Table of Assessments

Assessment/Activity	Associated CRF	Pre-Screening	Screening	Baseline	Randomization	Week 0 (induction)	Week 1	Week 4	Week 8	Week 12	Week 16	End of Treatment (≠Week 16)	As Needed Only
Inclusion/Exclusion checklist	ENR-B				X								
Informed Consent/HIPAA	ENR-A		X										
Inventory Form	INV												X
Locator Form			X	X	X	X	X	X	X	X	X	X	
Master Enrollment Log			X	X									
Medical Release			X										X
Missed Visit Form	MFV												X
Pre-Screening Interview	PSI	X											
Progress Note Checklist			X	X	X	X	X	X	X	X	X	X	
Protocol Deviation	PDV												X
Screening Log		X											
Study Termination	STT										X	X	
Visit Compensation Log			X	X	X	X	X	X	X	X	X	X	
General Measures													
Demographics	DEM		X										
Quality of Life, from PhenX	QLP			X							X	X	
Tobacco Use History, from PhenX	TUH			X							X	X	
Safety & Medical Measures													
Adverse Events	AD1-3												X
ARV Medication Log	ARV			X							X	X	
CBC	LAB		X										
CD4 Count	LAB				X			X		X	X	X	
Confirmed Pregnancy and Outcome	PRG,PO1- 4												X
Detoxification	DTX					X							

Assessment/Activity	Associated CRF	Pre-Screening	Screening	Baseline	Randomization	Week 0 (induction)	Week 1	Week 4	Week 8	Week 12	Week 16	End of Treatment (≠Week 16)	As Needed Only
ECG Results	ECG		X										
Ethyl Glucuronide	UDS		X				X	X	X	X	X	X	
Fatal Overdose	FOD										X	X	
Vital Signs (blood pressure, pulse, temperature, height, and weight)	VIS		X								X	X	
Hepatitis B surface antigen (HBs AG)	LAB				X								
Hepatitis C virus antibody (HCV ab)	LAB				X								
Hepatitis C pcr confirmation, when HCV ab +	LAB												X
HIV-1 RNA PCR	LAB				X			X	X	X	X	X	
Injection Site Abnormality	INA												X
Injection Site Examination	INX						X	X	X	X	X	X	
LFT (AST, ALT) and INR	LAB		X				X	X	X	X	X	X	
Medical and Psychiatric History	MHX		X										
Medication Adherence	MAD			X				X	X	X	X	X	
Pain Assessment	PEG			X				X	X	X	X	X	
Naloxone Challenge	NXC					X*							
Non-Fatal Overdose	NFO			X							X	X	
PBMC	LAB				X			X					
Physical Examination	PEX		X										
Pregnancy and Birth Control Assessment	PBC		X			X	X	X	X	X	X	X	
UDS	UDS		X			X	X	X	X	X	X	X	
XR-NTX administration log	INJ					X		X	X	X			
XR-NTX Injection						X		X	X	X			
Drug Use, HIV & Psychological Measures													
ASI Lite Drug/Alcohol Use	ASD			X							X	X	
Concise Health Risk Tracking	CHRT			X		X	X	X	X	X	X	X	

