17.2 Secondary Outcome Measures

1) HIV outcomes:

- a) HIV-1 RNA viral suppression (plasma HIV-1 RNA pcr \leq 200 copies/mL) at 16 weeks compared with screening (binary, laboratory assay).
- b) Change in CD4 count at the week 16 visit compared with screening (count; laboratory measurement).

2) Substance Use:

- a) Change in 30 day opioid abstinence (by Addiction Severity Index (ASI)-lite self-report, TLBF (self-report) and urine drug screen (UDS) confirmation) in the final 30 days of the 16 week trial compared to screening (binary; laboratory data and self-report).
- b) Change in past 30-day alcohol and other drug use by ASI-lite and UDS at week 16 visit compared to screening (binary; laboratory data and self-report).

3) Engagement in HIV Care:

- a) Change in the proportion of participants prescribed ART within 16 weeks following randomization, compared to baseline (binary; medical record abstraction).
- b) Proportion of participants taking 100% of prescribed ART doses in the past 3 days at 16 weeks for those prescribed ART at any point during the 16 week trial (proportion; self-reported ACTG adherence measure).
- c) Number of HIV primary care visits at 16 weeks (count, chart abstraction).

4) Participant safety:

- a) Change in liver enzymes between screening and week 16 visit (laboratory assay).
- b) Any fatal and non-fatal opioid overdose between screening and week 16 visit (binary; medical record abstraction and self-report).
- c) Change in Concise Health Risk Tracking score between screening and week 16 visit (continuous; self-report).
- d) Proportion of participants assigned to XR-NTX who develop precipitated opioid withdrawal.

Sample Size and Duration of Randomized Pilot Study Recruitment Phase

The randomized pilot study will recruit until either 50 participants have been enrolled or 12 months of recruitment have elapsed, whichever comes first. Justification for this decision follows:

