- a) Change in liver enzymes between baseline and 16 weeks or last lab measurement (*continuous; laboratory assay*). *Analysis via paired t-test, or analysis of change via ordinary least squares.*
- b) Any fatal and non-fatal opioid overdose at 16 weeks (*binary; medical record abstraction and self-report*). *Chi-squared test or logistic regression.*
- c) Change in Concise Health Risk Tracking score at 16 weeks compared to baseline (*continuous; self-report*). *Analysis via paired t-test, or analysis of change via ordinary least squares.*
- d) Proportion of participants assigned to XR-NTX who develop precipitated opioid withdrawal.

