23.1.5.5 Study Specific Risks

XR-NTX blocks the effects of exogenous opioids after administration. After treatment, participants are likely to have reduced tolerance to opioids. Following Vivitrol® treatment, opioid use at the end of a dosing interval or after missing a dose could result in potentially life- threatening opioid intoxication (involving respiratory compromise or arrest, circulatory collapse, etc.) Attempting to overcome the blockade effects of Vivitrol® by administering large amounts of exogenous opioids is associated with potential risk of overdose. Participants in this study will receive an information card that will notify clinicians that they are receiving XR-NTX as part of a research study.

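### The non-fatal overdose form asks about only 4 of a completer's 16 treatment weeks, although the outcome runs from screening to week 16

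*Protocol*

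**What the plan says.** **Outcome.** Sections 5.2, 8.2 and 17.2 define the same safety outcome. In section 17.2 it reads "Any fatal and non-fatal opioid overdose between screening and week 16 visit (binary; medical record abstraction and self-report".

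**Overdose form.** Section 15.2 states "Non-fatal overdoses in the past 4 weeks will be assessed using a self-reported instrument used in previous studies at baseline and 16 weeks" and then adds "or the end-of-medication visit (if medication is stopped early". In Table 10.1 the "Non-Fatal Overdose" row is marked at Baseline, Week 16 and the separate End of Treatment column. It is blank at weeks 0, 1, 4, 8 and 12 and under As Needed Only.

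**Other sources.** Section 9.2.5 lists overdose events among the items abstracted from records, up to 24 weeks after randomization. Section 15.1 has staff ask an open question at each visit about how the participant has felt since the previous one. Section 15.3 adds chart and locator-contact checks, for fatal overdose only.

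**Risk period.** Section 23.1.5.5 warns that "opioid use at the end of a dosing interval or after missing a dose could result in potentially" life-threatening intoxication.

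**The concern.** A form with a 4-week look-back, given once after baseline, cannot supply the self-report for an outcome spanning 17 to 24 weeks. The gap matters because section 23.1.5.5 ties overdose risk to particular times: the end of a dosing interval and the period after a missed dose.

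For a participant still on XR-NTX with an on-time week 12 injection, the only treatment weeks asked about are the four after that injection. Section 4.2 describes essentially complete blockade for 30 days after a dose. Induction, and the time around any earlier late or missed dose, fall outside the look-back. TAU participants have no corresponding pattern, so under-capture may differ between arms, in a direction the documents do not settle.

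Aim 4 Objective B is to supply safety point estimates for the multisite trial. An overdose that was never asked about cannot be recovered at analysis.

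**Working it through.** **Inputs**
- Screening s = 1 to 4 weeks, detoxification and induction d = 0 to 4 weeks, treatment 16 weeks (table in section 9.2).
- Look-back 4 weeks, at baseline and week 16 (section 15.2, Table 10.1).
- Injections at weeks 0, 4, 8 and 12 (section 9.3.3.3). A missed dose may be restarted up to 3 weeks after its scheduled date (section 9.3.3.4).

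**The plan's own figure.** Total duration = s + d + 16. The minimum is 1 + 0 + 16 = 17 and the maximum 4 + 4 + 16 = 24 weeks, matching the stated 17 to 24.

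**Completers, treatment period.** The week 16 look-back reaches weeks 12 to 16. Unasked = (16 − 4)/16 = 12/16 = 75%.

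**Completers, from randomization.** Unasked = (d + 12)/(d + 16): 12/16 = 75% at d = 0 and 16/20 = 80% at d = 4.

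**Completers, full outcome window.** Credit the baseline form with all of screening, which is generous. Unasked = (d + 12)/(s + d + 16):

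| s | d | Window (weeks) | Unasked (weeks) | Share |
|---|---|---|---|---|
| 1 | 0 | 17 | 12 | 70.6% |
| 1 | 4 | 21 | 16 | 76.2% |
| 4 | 0 | 20 | 12 | 60.0% |
| 4 | 4 | 24 | 16 | 66.7% |

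**Early stoppers.** With the last injection at week L, a 4-week dosing interval ends at L + 4 and 16 − (L + 4) weeks remain. For L = 0, 4 and 8 that is 12, 8 and 4 weeks. How much of this the form reaches depends on two things the protocol leaves open:
- End-of-medication form only, at the missed dose: 0 of the remaining weeks.
- End-of-medication form only, 3 weeks later: 3 of 12, 3 of 8 or 3 of 4.
- Week 16 form as well: 4 to 7 of 12, 4 to 7 of 8, or 4 of 4.

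**Illustration.** The documents give no overdose rate, so assume a 16-week risk R of 2 to 20%, constant hazard, and 50 completers. The risk inside a 4-week look-back is 1 − (1 − R)^(4/16).

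| R | Expected with an overdose | Expected with one inside the look-back |
|---|---|---|
| 2% | 1.0 | 0.25 |
| 5% | 2.5 | 0.64 |
| 10% | 5.0 | 1.30 |
| 20% | 10.0 | 2.71 |

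The form would reach about 25 to 27% of affected participants. At R = 5%, the chance that the look-back contains no overdose in any of the 50 is 0.95^12.5 = 0.53, against 0.95^50 = 0.08 that there truly was none.

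**The case against.** The strongest reply is that the form is only one source. The outcome combines record abstraction with self-report, abstraction explicitly includes overdose events, adverse events are solicited at every visit, and adverse event follow-up runs to 30 days after the last study visit (section 22.4). This stands in part. A reader might infer that only a quarter of overdoses would be counted; the documents do not support that, because 25% is the coverage of one form and not of the outcome. But section 9.2.5 describes abstraction as corroborating self-report, and it cannot find an event that never reached care. The adverse event question does not mention overdose. Section 19.5 also puts hospitalizations and deaths on study-specific forms instead of the adverse event form, while sections 15.2 and 15.3 want overdoses on the adverse event form too.

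A reader might also infer that nobody who stops early is asked about the time after stopping. That requires the alternative in section 15.2 to be exclusive. Sections 11.6 and 11.7 treat the two visits as alternatives, but for other forms. Table 10.1 marks both columns, and section 9.7 keeps all participants in follow-up. This is an ambiguity, not established zero coverage.

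A third inference is that the liver outcome has the same flaw and needs a peak-value endpoint above 5 times the upper limit of normal. The liver samples are drawn at weeks 1, 4, 8 and 12, and clinically significant laboratory changes count as adverse events (section 22.1), which section 17.8 reports by arm. The two elevations in 114 patients described in section 4.1 were below 5 times the limit, so that endpoint would have counted neither. What remains is wording: Aim 4 in section 2.1 promises "safety (percent with precipitated withdrawal, hepatotoxicity, or overdose" as percentages, whereas section 17.5 analyses "Change in liver enzymes between baseline and 16 weeks or last lab measurement".

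Finally, this is a feasibility pilot of at most 50, and section 17.5 treats secondary results as hypothesis-generating. That lowers the severity but does not justify the mismatch.

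**Conclusion.** The mismatch is real and internal to the protocol. For completers, the only overdose-specific self-report leaves 12 of 16 treatment weeks (75%) unasked, plus any induction period. Over screening to week 16 the unasked share is 60 to 76%. These shares follow from the stated schedule and assume that the baseline form covers all of screening. The event counts above also rest on an assumed risk and a constant hazard, so they are illustrative only.

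Total under-capture across all sources cannot be quantified from the documents. A difference between arms is plausible but not shown. For early stoppers, the protocol must state which visits carry the form. The point should be fixed before enrolment, but as a secondary outcome in a small pilot it does not endanger the primary aims.

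**What to change.** - Give the overdose form at weeks 0, 4, 8, 12 and 16. Ask about the time since the form was last completed. Naming the form, not the visit, matters because the week 1 visit would otherwise cut the week 4 recall short. For participants attending these visits, treatment-period coverage rises from 4/16 (25%) to 16/16 (100%), and week 0 closes the induction gap.
- State in section 15.2 that anyone who stops early completes the form at the end-of-medication visit, or its TAU equivalent, and at each later scheduled visit through week 16. Align Table 10.1, and reconcile with sections 9.7, 11.6 and 11.7.
- Reconcile section 19.5 with sections 15.2 and 15.3 on which form records an overdose that leads to hospitalization or death.
- Reconcile the hepatotoxicity percentage in section 2.1 with the change in liver enzymes in sections 8.2 and 17.5.

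The cost is one short form, a few minutes of interview each time, at visits that already exist.
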